##### **7.3.1.1. Adverse events**

Please refer to [Section 9](#) for the definition of non-serious and serious adverse events (SAEs).

Any AEs observed and reported within the reporting period will be recorded on the CRF by the investigator, regardless of the causal relationship with Xeljanz (see [Section 9.2](#)). The AEs can be reported by the patients. The investigator will also collect AE data by asking the patient questions such as “Have you had any health problem since the last visit?”

Check either “yes” or “no” in the AE section of CRF. If “yes”, record the following information:

Event name: Record the name of the AE according to the Korean Version of World Health Organization - Adverse Reaction Terminology (WHO-ART) distributed by Korean Ministry of Health and Welfare. If there is no not an appropriate term in the WHO-ART, record the name of the AE according to the Medical Terminology Dictionary written by the Korean Medical Society. If possible, specify diagnosis, not individual symptoms.

Date of onset: Record the onset date of the AE. Record approximate date if an actual date is unknown.

Date of recovery: Record the stop date of the AE if the outcome of the AE is recovered or recovered with sequelae (see below). Record approximate date if an actual date is unknown.

Seriousness: Check either “yes” or “no” to indicate if the event is a SAE. If “yes” record appropriate category of the seriousness (see [Section 9](#) for the definition and reporting of SAEs).

**Severity:** Evaluation of AE severity must be done according to the following categories:

- Mild: Not causing any significant problem to the patient. Administration of medicinal product continues without dose adjustment.
- Moderate: Causes a problem that does not interfere significantly with usual activities or the clinical status. Dose of the medicinal product is adjusted or other therapy is added due to the AE.
- Severe: Causes a problem that interferes significantly with usual activities or the clinical status. The medicinal product is stopped due to the AE.

If the severity of an AE changes, the AE must be entered separately. Record the stop date of the previous severity and onset date of the new severity – along with completion of all other related items.

**Causality assessment:** The causal relationship of AEs to the medicinal product must be allocated by the investigator according to the following criteria in alignment with the requirements of MFDS:

- Certain

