4.4. Safety Endpoints

The incidence and number with 95% confidence interval for all adverse events/adverse drug reactions investigated within 6 months from initial dosing after at least 1 dose of Xeljanz® during the study.

- Seriousness
- Severity
- Causality assessment
- Action taken
- Outcome

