6.4. Safety Analyses

Safety analyses will be performed based on data of safety analysis set. All adverse events in CRF will be classified by System Organ Class (SOC) and Preferred Term (PT) according to the latest version of MedDRA.

- 1) All adverse events investigated after administration of Xeljanz® during the study will be summarized by frequency and percent (n, percentage) by categorizing as follows. Also, it will be presented in n, incidence rate, 95% confidence interval of incidence rate and number of events for each SOC and PT.
 - Frequency analysis of adverse events/adverse drug reactions
 - Frequency analysis of serious adverse events/serious adverse drug reactions
 - Frequency analysis of serious unexpected adverse events/serious unexpected adverse drug reactions
 - Frequency analysis of unexpected adverse events/unexpected adverse drug reactions
 - Frequency analysis of adverse events of special interest/adverse drug reactions of special interest
 - Occurrence status of adverse events/adverse drug reactions by its seriousness
 - Results in death
 - Is life-threatening
 - Requires inpatient hospitalization or prolongation of hospitalization
 - Results in persistent or significant disability/incapacity
 - Results in congenital anomaly/birth defect
 - Important medical event: if it is determined that the event may jeopardize the patient or may require intervention to prevent one of the other outcomes listed in the definition above
 - Occurrence status of adverse events/adverse drug reactions by its severity
 - Mild
 - Moderate
 - Severe
 - Occurrence status of adverse events/adverse drug reactions by its causality assessment
 - Related to this medicinal product: ① Certain

Statistical Analysis Plan

- ② Probable/likely
- ③ Possible
- ⑤ Conditional/unclassified
- ⑥ Unassessable/unclassifiable

- Not related to this medicinal product: ④ Unlikely
- Occurrence status of adverse events/adverse drug reactions by its action taken
 - Permanently discontinued
 - Temporarily discontinued or delayed
 - Dose reduced
 - Dose increased
 - No change
 - Not applicable
- Occurrence status of adverse events/adverse drug reactions by its outcome
 - Recovered
 - Recovered with sequelae
 - Recovering
 - Not recovered
 - Unknown

2) Occurrence status of adverse events by demography and baseline characteristics

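### An AE that changes severity is entered on the CRF as a further AE record, and the SAP has no rule for counting these records as one event

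*Protocol*

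**What the plan says.** Protocol 7.3.1.1, under severity, sets the recording rule: "If the severity of an AE changes, the AE must be entered separately". It continues: "Record the stop date of the previous severity and onset date of the new severity – along with completion of all other related items". Each change of grade therefore produces a further full record with its own dates, seriousness, causality, action taken and outcome.

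SAP 6.4 sets the counting rule. Its source is the CRF: "All adverse events in CRF will be classified by System Organ Class (SOC) and Preferred Term (PT) according to the latest version of MedDRA". Item 1 then asks for n, the incidence rate, and the "95% confidence interval of incidence rate and number of events for each SOC and PT". The same item calls for "Occurrence status of adverse events/adverse drug reactions by its severity", with matching tables for seriousness, causality, action taken and outcome. Items 5 and 6 ask for event counts again in special populations and in off-label patients.

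SAP 4.4 describes the safety endpoint as "The incidence and number with 95% confidence interval for all adverse events/adverse drug reactions" within 6 months of the first dose. Protocol 7.7.1 names the incidence of AEs, with a 95% confidence interval, as the primary interest.

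Neither document defines an event, asks for an identifier linking records of one AE, or gives a worst-grade or last-outcome convention. SAP 5.1 deals only with missing data and the treatment stop date.

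**The concern.** The two rules are each reasonable but do not fit together. Splitting an AE by grade preserves its course. Counting all CRF AEs is the usual starting point for a safety table. Applied in sequence with nothing between them, they let one clinical event appear as two or more.

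The outputs exposed are the event counts by SOC and PT and any table built from records. One AE could stand under both mild and severe, or under two different actions taken. The outcome table gains a row for a segment that closed only because the grade changed, while the AE itself went on. Two programmers could also report different counts from the same database, and both would be following the SAP.

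Grade changes are also tied to management of the AE. The Protocol 7.3.1.1 scale links mild to unchanged treatment, moderate to a dose adjustment or added therapy, and severe to stopping the product. An AE first recorded as mild can therefore change grade, and generate a new record, when its management changes.

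**Working it through.** The plan states no figure on this point, so there is nothing to reproduce. The check follows one AE through the two rules and then sizes the effect under stated assumptions.

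**Step 1: records per event.** An AE that changes grade k times yields 1 + k records under Protocol 7.3.1.1.

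**Step 2: inflation factor.** Let f be the share of AEs that change grade and k the number of changes in each of those. Then

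records ÷ true events = 1 + f × k.

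Both f and k are assumptions.

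| f (assumed) | k = 1 | k = 2 |
|---|---|---|
| 5% | 1.05 | 1.10 |
| 10% | 1.10 | 1.20 |
| 20% | 1.20 | 1.40 |
| 30% | 1.30 | 1.60 |

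With k = 1 the overstatement equals f, so the table shows only how an assumption translates into a count. It does not estimate what this study will see.

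**Step 3: effect on the severity table (assumed example).** Take 100 true AEs with worst grade mild/moderate/severe of 80/15/5. Suppose that 10 of the 20 moderate or severe AEs began as mild (f = 10%, k = 1).

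- Records: mild 80 + 10 = 90, moderate 15, severe 5; total 110.
- Event count: 110 ÷ 100 = 1.10, which is 10% too high.
- Mild share: 80 ÷ 100 = 80% becomes 90 ÷ 110 = 81.8%.
- Severe share: 5 ÷ 100 = 5.0% becomes 5 ÷ 110 = 4.5%.

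With one change per event, the extra record is always below the worst grade, so the severe share falls. With repeated changes (severe, mild, severe) a worst-grade record can itself be duplicated, so the direction for the severity mix is not guaranteed. The direction for the total count is: it can only rise.

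**Step 4: effect on incidence.** If n is the number of patients with at least one event of a given SOC or PT, a second record for the same AE adds no patient. Incidence and its 95% confidence interval do not change. SAP 6.4 lists n separately from the number of events, which favours this reading, but does not define n. Even in a severity table that counts patients, a patient could appear under two grades for one AE unless a worst-grade rule applies.

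**The case against.** The strongest reply is that the double count is inferred. SAP 6.4 speaks of events, not records, and Protocol 7.3.1.1 itself treats the case as one AE with two entries. A competent programmer may merge them, and the CRF layout, which is not in the documents, might link them. This stands in part: the inflation is conditional on counting records as entered. But the SAP takes all CRF AEs as its source, and no text requires merging.

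A second reply is that the primary interest is untouched. This stands if n means patients. A reader might infer from SAP 4.4 that event counts are formally part of the endpoint, but that section does not say whether its number refers to patients or events.

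A third concerns outcome. Protocol 7.3.1.1 tells the investigator to give a stop date when the AE has recovered, with or without sequelae, and the severity rule also demands a stop date for the earlier grade. A reader might infer that worsening AEs will produce false 'recovered' rows. The documents do not support this. The first instruction does not restrict stop dates to recovered AEs. The second dates a grade rather than a recovery, and 'recovering' and 'not recovered' are both available. What remains is an extra outcome row of unknown category.

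Finally, captured grade changes may be uncommon: 6 months of observation, no mandated visits, partly retrospective collection and a three-level scale. That is plausible and bears on size, which the documents leave open.

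**Conclusion.** The concern holds in conditional form. If the CRF records are counted as entered, the event counts in SAP 6.4, and the tables of seriousness, severity, causality, action taken and outcome where they are built from records, are inflated by the factor 1 + f × k. The range of 1.05 to 1.60 rests wholly on assumed values (f from 5% to 30%, k of 1 or 2) and should not be read as a forecast.

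The incidence of AEs, its confidence interval, and the subgroup tests and logistic regression in SAP 6.4 do not change, provided that they count patients with at least one event. This is a defect in supporting descriptive tables of a study whose main interest is safety. It should be corrected because the written recording and counting rules together produce it, and the correction is cheap.

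**What to change.** Add to SAP 6.4:

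- n and the incidence rate count patients with at least one event in the category; the number of events is reported separately.
- Records of the same PT in the same patient that arise from a change of severity count as one event. They are identified from contiguous stop and onset dates. Because Protocol 7.3.1.1 allows approximate dates, same-PT records within a patient are also reviewed in a listing before database lock.
- The event takes the worst severity, the most serious classification, the strongest causality, the most consequential action taken on any of its records, and the outcome of the last record.

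Action taken should not come from the last record. An AE graded severe, with the product stopped, may improve to mild, and its last record may show no change. Using that record would lose a discontinuation or dose reduction and contradict the severe grade. The SAP should state the ranking of actions; the order in which SAP 6.4 already lists them could serve.

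The separate CRF entries can stay as they are, and no new data are needed. The cost is a short SAP addition, a small programming step and the listing review. Date matching alone may miss some pairs or join distinct episodes, which is why the review is needed.

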### 7.3.1.2. Laboratory test

Recommended laboratory tests and time points are included in Table 1. Test results of chest X-ray, erythrocyte sedimentation rate (ESR), C-reactive protein (CRP), other blood chemistry, hematology, and tuberculin test should be recorded, if conducted.

**Table 1 Recommended Laboratory Test**

	Lymphocyte	Neutrophils	Hemoglobin	Lipids (TC, HDL, LDL)
Baseline	√	√	√	√
4 to 8 weeks after treatment		√	√	√
Every 3 months	√	√	√	

Abbreviations: TC=total cholesterol, HDL= high density lipoprotein, LDL=low density lipoprotein.

In case there are any clinically significant laboratory abnormalities (as per the investigator's judgment) that occur after the treatment of Xeljanz compared to baseline, the tests should be recorded in detail on the CRF, including the laboratory normal ranges of the center, test results before and after Xeljanz treatment, a causal relationship to Xeljanz, and any comments from the investigator.

According to Contraindication on label, the investigator should discontinue the patient's treatment if the laboratory test results are as below

- Patients with an absolute neutrophil count (ANC) <500 cells/mm^3\*
- Patients with a hemoglobin level <8 g/dL

Please refer to [Section 9.4.1](#) for the criteria for determining whether an abnormal objective test finding should be reported as an AE.

### 7.3.2. Efficacy variables

Efficacy variables include DAS28, EULAR response, and ACR20 response. The investigator can make an assessment of the overall efficacy – improved, no change, aggravated - based on each test results and clinical judgment.

#### 7.3.2.1. Efficacy evaluation

Efficacy assessment will be performed by the accredited investigator in the Korean health care center. In the case of RA, The investigator will perform the efficacy assessment at baseline and after 6 months of treatment by any of the commonly used efficacy assessment criteria such

as DAS28 and American College of Rheumatology 20% improvement criteria (ACR20), and record the assessment results in each patient's CRF. If the patient dose not complete 6 months of treatment, relevant data should be collected based on the last assessment performed at the time of treatment discontinuation.

DAS28, a modified version of the original Disease Activity Score (DAS), is a quantitative measure of disease activity used to monitor the treatment of [RA](#). DAS28 is calculated using the following formula that includes the number of tender joints and swollen joints (28 joints maximum).

$$\text{DAS28 (ESR)} = 0.56 \times \sqrt{(\text{TJC 28})} + 0.28 \times \sqrt{(\text{SJC 28})} + 0.014 \times \text{VAS} + 0.70 \times \ln(\text{ESR})$$

[figure not shown]
or,

$$\text{DAS28 (CRP)} = 0.56 \times \sqrt{(\text{TJC 28})} + 0.28 \times \sqrt{(\text{SJC 28})} + 0.014 \times \text{VAS} + 0.36 \times \ln(\text{CRP}+1) + 0.96$$

Of which, CRP=C-reactive protein, ESR=erythrocyte sedimentation rate, SJC28=28 swollen joint count, TJC28=28 tender joint count, VAS=visual analogue scale

The DAS-based EULAR response criteria (see Figure 1) classify individual patients as none, moderate, or good responders, depending on the extent of change and the level of disease activity reached.

**Figure 1 DAS28-based EULAR response criteria**

An ACR20 response is defined as at least 20% improvement in both the tender joint count and the swollen joint count and at least 20% improvement in 3 of the 5 other disease activity measures (items 3 to 7) listed in [Table 2](#). If ACR20 is assessed in the usual clinical practice, the results should be recorded as “done-achieved” or “done-not achieved”. If ACR20 is not assessed, the investigator records “not done” in the CRF.

In the case of PsA, the number of active joints, including number of tender and swollen joints at 3 months of treatment is measured. DAS28 can be calculated based on the number of active joints, and DAS28 calculation is the same as calculation of RA above.

**Table 2 American College of Rheumatology Preliminary Definition of Improvement in Rheumatoid Arthritis**

**Disease activity measures:**

1. Tender joint count
2. Swollen joint count
3. Patient's assessment of pain
4. Patient's global assessment of disease activity
5. Physician's global assessment of disease activity
6. Patient's assessment of physical function
7. Acute-phase reactant value: ESR or CRP level

Abbreviations: CRP=C-reactive protein, ESR=erythrocyte sedimentation rate.

## **7.4. Data sources**

### **7.4.1. Case report forms**

As used in this protocol, the term CRF should be understood to refer to either a paper form or an electronic data record or both, depending on the data collection method used in this study.

A CRF is required and should be completed for each included patient. The completed original CRFs are the sole property of Pfizer and should not be made available in any form to the third parties, except for authorized representatives of Pfizer or appropriate regulatory authorities, without written permission from Pfizer. The investigator shall ensure that the CRFs are securely stored at the study site in encrypted electronic form and will be password protected to prevent access by unauthorized third parties.

The investigator has ultimate responsibility for the collection and reporting of all clinical, safety, and laboratory data entered on the CRFs, any other data collection forms (source documents) and ensuring that they are accurate, authentic/original, attributable, complete, consistent, legible, timely (contemporaneous), enduring, and available when required. The CRFs must be signed by the investigator or by an authorized staff member to attest that the data contained on the CRFs are true. Any corrections to entries made on the CRFs or source documents must be dated, initialed and explained (if necessary) and should not obscure the original entry.

In most cases, the source documents are the hospital's or the physician's patient chart. In these cases data collected on the CRFs must match the data in those charts.

In some cases, the CRF may also serve as the source document. In these cases, a document should be available at the investigator site and at Pfizer that clearly identifies those data that will be recorded on the CRF, and for which the CRF will stand as the source document.

### **7.4.2. Record retention**

To enable evaluations and/or inspections audits from regulatory authorities or Pfizer, the investigator agrees to keep records, including the identity of all participating patients (sufficient information to link records, eg, CRFs and hospital records), all original signed

[figure not shown]
informed consent documents copies of all CRFs, safety reporting forms source documents, and detailed records of treatment disposition, and adequate documentation of relevant correspondence (eg, letters, meeting minutes, telephone calls reports). The records should be retained by the investigator according to local regulations, or as specified in the Clinical Study Agreement, whichever is longer. The investigator must ensure that the records continue to be stored securely for so long as they are retained.

If the investigator becomes unable for any reason to continue to retain study records for the required period (eg, retirement, relocation), Pfizer should be prospectively notified. The study records must be transferred to a designee acceptable to Pfizer, such as another investigator, another institution, or to an independent third party arranged by Pfizer. Investigator records must be kept for a minimum of 15 years after completion or discontinuation of the study or for longer if required by applicable local regulations.

The investigator must obtain Pfizer's written permission before disposing of any records, even if retention requirements have been met.

CCI

CCI

## **7.6. Data management**

CRF data collected by the investigator will be entered into the clinical database. Verifications will be performed after comparison of the double data entry. All missing data or data to be checked will be reported on a query sheet for further verification at the study site. Any data modification will be recorded.

AEs and Medical history will be coded using MedDRA(Medical Dictionary for Regulatory Activities). Concomitant medication will be coded via ATC code.

Statistical analysis will be carried out with SAS software version 9.2 or a more recent version.

## **7.7. Data analysis**

Analysis will be performed for the pooled data collected by each investigator during the re-examination period. Total number of centers participating, total number of cases enrolled and retrieved, and total number of cases included in the analysis will be presented in summary tables. Evaluation of data will primarily consist of summary displays (eg, descriptive statistics, tables, and graphs).

Detailed methodology for summary and statistical analyses of data collected in this study will be documented in a Statistical Analysis Plan (SAP), which will be dated, filed and maintained by Pfizer. The SAP may modify the plans outlined in the protocol; any major modifications of primary endpoint definitions or their analyses will be reflected in a protocol amendment.

### **7.7.1. Safety analysis**

[figure not shown]
The primary interest of this study is the incidence of AEs investigated during the re-examination period. Incidence of each AE will be presented with 95% confidence interval. Serious, related, and/or unexpected AEs will be summarized separately.

To identify the factors that affect safety, subgroup analysis for various factors will be performed, including the classification of AEs by body system, and comparison of incidence of AEs by sex, age, presence of concurrent diseases, presence of concomitant medications, baseline disease activity, etc.

In case the drug was administered to special populations such as children, elderly people, or patients with renal or hepatic disorders during the study, subgroup analysis will also be performed for each of those populations.

Unexpected AEs/ADRs will be classified by medical review with reference to the local product document. Events already included in the “Precautions for use” section of the local product document will be classified as “expected”. All other events that are not included in the “Precautions for use” section of the local product document will be classified as “unexpected”. An unexpected AE includes any events that may be symptomatically and patho-physiologically related to an event listed in the labeling, but differs from the labeled event because of greater severity or specificity.

In the case of an adverse event with important potential risks and important identified risks in relation to the safety specification under the risk management plan, or if missing information patient group is recruited, actions according to the label will be taken, and the safety information is presented separately.

